Statistical Design and Power for Proposed Pilot Study: Family-Authored ICU Diaries to Reduce Fear in Patients Experiencing a Cardiac Arrest (FAID Fear)

NCT Number: NCT05144477

Document Date: 2/26/2021

Statistical Design and Power for Proposed Pilot Study: Family-Authored ICU Diaries to Reduce Fear in Patients Experiencing a Cardiac Arrest (FAID Fear): A Pilot Intervention Study

Aim 1: Enroll 15 partners of cardiac arrest (CA) patients and surviving patients to (a) pilot recruitment procedures, (b) estimate retention, and (c) assess acceptability of study procedures for both family members and patients in the intervention condition.

Aim 1 will be tested by assessing the following measures:

OUTCOME MEASURES

- 1) Proportion of eligible *partners* of cardiac arrest (CA) patients whom we approach who enroll in the pilot study.
- 2) Proportion of enrolled *partners* who complete the pilot study outcome assessments one month following either the death of the patient or patient discharge from the ICU.
- 3) Proportion of *partners* that adhere to the diary intervention (complete ≥ 2 diary entries/week).
- 4) Proportion of *partners* that agree that the intervention was acceptable using the mean of the 4-item Acceptability of Intervention Measure (score ≥ 4 ; 1 = *completely disagree*, 5 = *completely agree*).
- 5) Proportion of *partners* that agree that the intervention was feasible using the mean of the 4-item Intervention Feasibility Measure (score ≥ 4 ; 1 = *completely disagree*, 5 = *completely agree*).
- 6) Proportion of *partners* that agree that the intervention was appropriate for reducing cardiac anxiety about the patient's heart using the mean of the 4-item Intervention Appropriateness Measure (score ≥ 4 ; 1 = *completely disagree*, 5 = *completely agree*).
- 7) Proportion of eligible CA *patients* whom we approach who ultimately agree to participate in the pilot study.
- 8) Proportion of enrolled CA *patients* who complete the outcome assessments one month following discharge from the ICU.

Statistical approach for Aim 1. We will compute the proportions listed above, including 95% confidence intervals.

Aim 2: Obtain an estimate of the association of intervention v. control with (i) partner and patient fear (operationalized as cardiac anxiety about the patients' cardiac condition) at hospital discharge and (ii) partner

and patient posttraumatic stress symptoms (PTSS) 30 days post-discharge. Obtain an estimate of the longitudinal association between partner fear during ICU stay with patient fear at discharge and patient and partner posttraumatic stress symptoms (PTSS) at 30 days post-discharge.

Aim 2 will be tested by assessing the following measures:

- 9) Intervention v. control difference in *partners'* cardiac anxiety about the patients' heart at discharge, measured as the mean of the 8-item fear subscale of the Cardiac Anxiety Questionnaire.
- 10) Intervention v. control difference in *CA patients'* cardiac anxiety about the patients' heart at discharge, measured as the mean of the 8-item fear subscale of the Cardiac Anxiety Questionnaire.
- 11) Intervention v. control difference in *partners'* posttraumatic stress symptoms in relation to the patients' cardiac arrest at one month post-discharge, measured as the sum of the 20-item Posttraumatic Stress Disorder Checklist.
- 12) Intervention v. control difference in *CA patients'* posttraumatic stress symptoms in relation to the patients' cardiac arrest at one month post-discharge, measured as the sum of the 20-item Posttraumatic Stress Disorder Checklist.
- 13) Correlation between *partners'* cardiac anxiety about the patients' heart at discharge and *CA patients'* cardiac anxiety about the patients' heart at discharge
- 14) Correlation between *partners'* cardiac anxiety about the patients' heart at discharge and *CA patients'* posttraumatic stress symptoms in relation to the patients' cardiac arrest at one month post-discharge

Statistical approach for Aim 2. We will compute **(2a)** the mean difference in cardiac anxiety and PTSS between intervention and control conditions and **(2b)** the correlation between partner cardiac anxiety during ICU stay with patient cardiac anxiety at discharge and patient and partner PTSS at 30 days. For each, the estimate – 1 standard error will be used for sample size calculations when planning the larger study to account for uncertainty in small samples. As mentioned above, this Phase-I feasibility trial is not powered to test the significance of these intervention v. control differences, or these patient-partner associations.

Exploratory Aims: **(1)** Obtain an estimate of the association of intervention v. control with partner and patient aversive cognitions towards exercise at hospital discharge. **(2)** Test feasibility of objective monitoring of patient physical activity during the first 30 days post-discharge.

- 15) Intervention v. control difference in *partners'* aversive cognitions towards patients' exercise at discharge, assessed using the mean of the 5-item avoidance subscale of the Cardiac Anxiety Questionnaire.
- 16) Intervention v. control difference in *CA patients'* aversive cognitions towards patients' exercise at discharge, assessed using the mean of the 5-item avoidance subscale of the Cardiac Anxiety Questionnaire.
- 17) Proportion of patients who wear the FitBit ≥ 10 hours for ≥ 4 days/week.

Statistical approach for Exploratory Aims. We will compute the mean difference in partner and patient aversive cognitions towards exercise at hospital discharge in intervention v. control conditions, and also the estimate – 1 standard error. We will compute the estimate – 1 standard error for FitBit wear time (days, hours).

Planned Interim Analyses. Given the relatively small sample size for this pilot ($N = 15$ participants) and the expected minimal risk, interim analyses are not planned. If concerns arise related to adverse events, as outlined in the data safety monitoring plan, then an unblinded interim analysis may be conducted, and the trial may be stopped prematurely.

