Partners/family members who undergo informed consent and agree to participate will be randomized 2:1 to either the ICU diary (intervention) or the control condition. Randomization will occur using opaque sealed envelopes to be opened by the study coordinator after consent is provided/document. The partner/family member participant will be informed of the randomization assignment and a baseline assessment will also occur.

Randomized to ICU Diary Condition

These partners/family members will receive standard contact and communication from ICU/hospital doctors.

Following the design of Nielsen et al.,²⁵ partners/family members will be provided with a hard-cover diary containing written instructions (diary instructions included in RASCAL attachments) and a pen. If consent and randomization occur in person, the diary will be handed to the participant. If consent and randomization occur by phone, the diary will either be mailed to the participant or the coordinator will arrange for a time to meet the participant in the hospital or at the CBCH offices to provide the diary. A trained research assistant will explain how to use the diary, and instructions will include recommended frequency for writing and tips on how to express themselves. The hard copy of the diary will remain with the partner/family member participant and they will be asked to continue writing in the diary until patient end of hospital care (e.g. ICU). The diary will not be collected at the conclusion of the study. Research assistants will check in with participants via weekly telephone calls to provide support, as needed, if the partner/family member reports difficulty in writing diary entries (e.g., suggesting the partner/family member write at home rather than in the hospital, encouraging use of key words or focusing on the present if events are hard to summarize).

We confirm that the hard-copy diary that is provided to subjects will not reference any identifiers or codes and the diary will NOT be collected back from participants as part of the study (once the blank diary is given to the participant, it is theirs to keep).

Randomized to Control Condition

These partners/family members will receive standard contact and communication from ICU/hospital doctors.

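### SAP measures 13-14 correlate post-diary partner and patient scores with no term for randomized arm, so the raw correlation can mix the diary effect with the partner-patient association (minor)

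*SAP*

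**What the plan says.** All the correlations are in the SAP under Aim 2.

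- Measures 9-12 are intervention-versus-control differences in partner and patient cardiac anxiety at discharge and in partner and patient PTSS at one month.
- Measure 13 is "Correlation between *partners'* cardiac anxiety about the patients' heart at discharge and *CA patients'* cardiac anxiety about the patients' heart at discharge". Measure 14 pairs the same partner discharge score with the patients' "posttraumatic stress symptoms in relation to the patients' cardiac arrest at one month post-discharge".
- The Aim 2 statement sets a different time point for the partner score: "Obtain an estimate of the longitudinal association between partner fear during ICU stay with patient fear at discharge". Item 2b of the statistical approach agrees with it and computes "the correlation between partner cardiac anxiety during ICU stay with patient cardiac anxiety at discharge and patient and partner PTSS at 30 days".
- The planning rule comes directly after 2a and 2b: "For each, the estimate – 1 standard error will be used for sample size calculations when planning the larger study".

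No correlation is described as partial, stratified or within-arm. The SAP does not use the word pooled, but on a plain reading each is one raw correlation over all available pairs.

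The allocation ratio is given only in the protocol (section 3, Study Procedures): participants who "agree to participate will be randomized 2:1 to either the ICU diary (intervention) or the control condition". The same section places the baseline assessment at about the time the participant is told the assignment.

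**The concern.** In measures 13-14 both variables are measured after randomization, and Aim 2 treats both as possible targets of the diary. Randomized arm may therefore be a common cause of the two. A mean shift between arms in both variables adds between-arm covariance to the raw correlation, even if partner and patient scores are unrelated within each arm.

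At stake is what the number means. The protocol's long-term question is whether lower fear in family members improves patients' wellbeing. A correlation offered as evidence of that link should not contain an unknown amount of the intervention's own effect. This issue is separate from the SAP's disagreement over which time point of partner fear to use, although the time point decides whether the issue arises.

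**Working it through.** **Figures in the plan.** The SAP gives no correlation, effect size, SD, alpha or power for Aim 2, so there is no figure of its own to reproduce. The within-arm correlation, effect sizes, alpha and power below are assumptions.

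**Inputs.** Allocation 2:1 (protocol), so p(1-p) = 2/3 × 1/3 = 0.2222. Planned size 15 (SAP) or up to 31 (protocol). Expected retention about 90% (SAP), so 0.90 × 31 = 27.9, about 28 completers. Assumed: within-arm correlation rho = 0.30, equal within-arm SDs, and standardized arm effects dx on the partner score and dy on the patient score.

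**Formula.** Raw r = (rho + 0.2222·dx·dy) / √[(1 + 0.2222·dx²)(1 + 0.2222·dy²)].

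**Results with rho = 0.30.**

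| Case | Calculation | Raw r |
|---|---|---|
| Both shift, d = 0.5 | (0.30 + 0.0556)/1.0556 | 0.337 |
| Both shift, d = 0.8 | (0.30 + 0.1422)/1.1422 | 0.387 |
| Patient effect only through partner fear (dy = 0.30·dx), dx = 0.5 | 0.3167/√(1.0556 × 1.0050) | 0.307 |
| Same, dx = 0.8 | 0.3427/√(1.1422 × 1.0128) | 0.319 |
| Only one variable shifts, d = 0.5 | 0.30/√1.0556 | 0.292 |
| Only one variable shifts, d = 0.8 | 0.30/√1.1422 | 0.281 |

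The bias is therefore conditional and can go either way. Upward bias needs effects in the same direction on both variables. With a high within-arm correlation and unequal effects it disappears: rho = 0.70 with d = 0.8 and 0.3 gives 0.698.

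**Simulation (40,000 replicates, rho = 0.30).** With both scores shifted by 0.5 or 0.8, mean raw r was 0.330 or 0.382 at 10:5, and 0.332 or 0.383 at 21:10. The arm-centred correlation averaged 0.289-0.292 at 10:5 and 0.293-0.296 at 21:10 in every case run, including the one-sided ones.

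**Cost in precision.** Estimating the arm means uses one degree of freedom, so the SE grows by about √[(N-1)/(N-2)]: √(14/13) = 1.038 at N = 15, and √(30/29) = 1.017 at N = 31. Where both scores shift, the simulated SD of the raw r looks smaller still (0.157 against 0.172 at 21:10, d = 0.8). That is partly because a larger r has a smaller SE, and the raw r is centred on the wrong value.

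**Does this reach the planning rule?** The rule follows 2a and 2b, and 2b uses ICU-stay partner fear. If that is the baseline score, dx is about 0 and the one-sided rows apply (0.281-0.292, slightly low).

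Suppose a measure 13-14 correlation were nevertheless carried forward. Take 28 completers, SE = (1 - r²)/√27, and N = [(1.960 + 0.842)/atanh(r)]² + 3 (two-sided 0.05, 80% power):

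- r = 0.30: 0.300 - 0.175 = 0.125, N about 501.
- r = 0.337: 0.337 - 0.171 = 0.166, N about 282.
- r = 0.387: 0.387 - 0.164 = 0.224, N about 155.

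Detecting a true r of 0.30 needs N = 85. The inflation uses up part of the intended margin, but the planned N stays above 85 in each case.

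**The case against.** A reader might infer that the inflated correlations feed the sample size of the larger study and would leave it too small. The documents do not support this, for four reasons.

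- The planning rule is attached to 2a and 2b, and 2b is not inflated if ICU-stay fear is measured at baseline.
- Subtracting one SE removes more than the inflation adds in the cases above.
- The SAP describes the next study as powered for reductions in cardiac anxiety, which is an arm difference. It does not say how a correlation would enter that calculation, so the Fisher-z sizes above are illustrative only.
- Equal effects on partner and patient are a favourable assumption. The earlier diary trial that the protocol cites reported PTSS 26.3% lower in family members but 11.2% lower in patients, with an interval that includes zero.

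It can also be said that, if the diary reaches patients only by lowering partner fear, the added covariance travels along the very link under study. In that case the shift is only 0.007 to 0.019.

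Finally, the measures may no longer be live. Patient measures are secondary in the SAP (2/26/2021). Aim 2 of the later protocol (7/5/2022) covers partner/family outcomes only. The protocol allows linkage to CANOE data, but neither document says that CANOE collects patient cardiac anxiety or PTSS.

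All of this stands, and it limits the point to the interpretation of measures 13-14. It does not remove it. The minus-1-SE rule is stated to allow for sampling uncertainty and is not a correction for bias. Nor do the documents say which of the cases above will apply, so a raw correlation could not be read as the within-arm association.

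**Conclusion.** The point holds as a minor one. Measures 13-14 are raw correlations between post-diary variables on which the same aim estimates arm effects, and no adjustment for arm is stated. Under the assumed rho of 0.30 and 2:1 allocation, the distortion runs from about -0.02 (only one score shifts) through +0.01 to +0.02 (effect through partner fear, d = 0.5-0.8) to +0.04 or +0.09 (d = 0.5 or 0.8 on both). These shifts are small beside the SE of r, (1 - 0.09)/√(N-1), which is about 0.24 at N = 15 and 0.17 at N = 31.

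For 2b, upward bias could arise only if ICU-stay fear is recorded after diary writing has begun, which the documents do not settle. No conclusion is drawn that the next study would be undersized. The point applies to the patient pairs only if they are still planned.

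**What to change.** Add one sentence to the SAP's statistical approach for Aim 2. For measures 13-14, and for 2b for consistency, compute each correlation adjusted for randomized arm (a partial correlation, or equivalently from deviations about each arm's mean), and report it with its SE and 95% CI. If any correlation is carried into planning, use the arm-adjusted value.

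Alongside this, the sponsor should state:

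- whether the partner-patient correlations are still planned under the later protocol and, if so, where the patient data come from;
- which time point of partner fear feeds planning, since 2b and the Aim 2 statement say ICU stay while measures 13-14 say discharge.

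The partner-only pair in 2b (ICU-stay partner fear with partner PTSS at 30 days) can be handled the same way whatever is decided about patients.

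The cost is one degree of freedom, an SE about 2-4% larger, and no new data.
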